Protocol Title: A Cross-over Pilot Trial to Determine the Effect of an LSU Patented Dietary Herbal Supplement on Quality of Life

PI Name: **[name]**

Sub-Investigator's Name(s): **[name]**

Protocol Version Date: **December 16, 2021**

IRB Review History

Modification 3

Objectives

Specific Aim 1: Compare the quality of life using the validated Chubon Quality of Life Rating scale after taking the supplement or the placebo at baseline followed by a 2-week washout, then 1 week taking the supplement or placebo that was not taken in the first period.

Specific Aim 2: Compare the safety of the supplement by evaluating questionnaires, chemistry panel, CBC, Janus 3, adverse events and polysomnography at baseline and after 1 week of nightly administration with the supplement or the placebo before and after a 2-week washout.

Hypothesis: The supplement will improve the quality of life compared to the placebo condition

Background

[name] and [name] at Louisiana State University Agricultural Center developed a novel dietary herbal supplement consisting of at least two components chosen from the following six foods. 1. Collagen peptides of less than 3500 Daltons and preferably less than 2,000 Daltons derived from animals like cows, or other glycine-rich peptides. 2. Theanine, a component of decaffeinated green tea. 3. lactucopicrin, deoxylactucopicrin or another lactucopicrin derivative found in chicory. 4. Hyaluronic acid, a component of cartilage. 5. epigallocatechin gallate, a component decaffeinated green tea. and 6. quinic acid found in chicory. This dietary supplement contains chicory and decaffeinated green tea containing epigallocatechin gallate. These ingredients are thought to decrease Janus kinase 3 (JAK-3) and people who have tried the supplement claim that it made them feel better, made them feel more alert and improved their quality of life.

This trial is designed to measure the quality of life in response to taking the novel supplement. People over 50 years of age with difficulty sleeping frequently feel tired and lack in energy which degrades their quality of life. We will test the effect of the dietary herbal supplement on quality of life using a validated questionnaire in humans with difficulty sleeping over 50 years of age compared to a placebo in a crossover trial

comparing the supplement to a placebo after 1 week of administration separated by a 2-week washout period.

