 - e. Daytime sleepiness.
 - f. Motivation, energy, or initiative reduction.
 - g. Proneness for errors or accidents at work or while driving.
 - h. Tension, headaches, or gastrointestinal symptoms in response to sleep loss.
 - i. Concerns or worries about sleep.

Subjects that meet the following criteria will be excluded from the study

1. Have diabetes.
2. Are taking sedating or hypnotic medications.
3. Taking any chronic medication for which the dose has not been stable dose for 1 month or longer.
4. Have a sleep disorder other than difficulty sleeping such as sleep apnea
5. Adults unable to consent
6. Individuals who are not yet adults (infants, children, teenagers)
7. Pregnant women
8. Prisoners

Number of Subjects

Ten subjects will be enrolled in this cross-over study consisting of a screening visit and four study visits

Recruitment Methods

The subjects will be recruited through the Pennington Advertising and Recruiting Departments and connections with [name] who is a sleep specialist.

We anticipate a successful recruitment from a past history of referrals from [name]

The advertisements will be developed by the marketing department and submitted for IRB review.

Study Timelines

The duration of each subject's participation will be approximately one month. There will be a 1-week period of taking the supplement or the placebo, a 2-week washout and another 1-week period of consuming the placebo or supplement not taken in the first arm of the crossover trial

The grant was issued in February of 2020 and should be completed within a year. The Covid-19 problem has delayed the start of the study, but we hope to complete the study by the end of 2022.

We anticipate finishing the trial in 12 weeks, if we enroll a subject each week. The primary analysis should be completed in the following 2 weeks and the report submitted to the Lift Grant Administration 4 weeks from the study completion.

Study Endpoints

Primary Endpoint:

1. The Chubon Quality of Life Rating Scale. This scale has a test-retest stability of 0.91, Chronbach's alpha for variety of group ranges from 0.74 to 0.95 for internal consistency (2).

Secondary Safety Endpoints:

1. The Insomnia Severity Index questionnaire
2. The Epworth Sleepiness Scale questionnaire
3. The Pittsburgh Sleep Quality Index questionnaire

4. Janus-3 kinase
5. Polysomnography
6. 7-day accelerometry
7. Chemistry panel and CBC
8. Adverse events

Procedures Involved

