Screening visit: Subjects will come to the screening visit having fasted for 10 hours except for water. Subjects will give informed consent, have vital signs height and weight measured, have blood drawn for a chemistry panel, CBC, complete a health questionnaire and complete the validated questionnaire, the Insomnia Severity Index. Subjects will have overnight oximetry to screen for sleep apnea rather than true difficulty sleeping. Subjects will be asked to wear an actigraphy to measure motion/activity during the day and night for 7 days. Subjects will be asked to keep a sleep diary for 7 days and return the diary, along with the actigraphy to the study staff for review. Those passing the screening visit will return for study visit one.

Study visit 1: Subjects will come to the sleep lab at 7:00 pm after having eaten dinner at home for an overnight polysomnography test that includes oximetry and actigraphy. Subjects will be asked to sleep from 10:00 pm to 6:00 am the next day. The following morning subjects will complete 5 validated questionnaires: the Insomnia Severity Index, the Epworth Sleepiness Scale, the Pittsburgh Sleep Quality Index, the Chubon Quality of Life Rating Scale, and the Multi-dimensional Fatigue Inventory. Unless a specific cause like sleep apnea is identified as the reason for the fatigue symptoms, the subjects will be given a week's supply of the dietary supplement or placebo with instructions to take 2 ounces an hour before bedtime. The study order of the supplement or placebo will be assigned randomly. Subjects will be asked to use actigraphy and keep a sleep diary for the 7-day period until their next visit.

Study Visit 2: The subject will return in 1 week (± 3 days) for a repeat polysomnography test, 1 hour before which the subject will take the assigned study supplement or placebo. Upon awakening the next morning, the subjects will have a blood drawn for a chemistry panel, a CBC and Janus kinase 3. Subjects will also have blood drawn to archive serum, buffy coat and EDTA plasma. On awakening the next morning they will be asked to complete the 5 validated questionnaires: Insomnia Severity Index, the Epworth Sleepiness Scale, the Pittsburgh Sleep Quality Index, the Chubon Quality of Life Rating Scale and the Multi-dimensional Fatigue Inventory.

After a **2-week washout period** subjects will return for visit 3.

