Study visit 3: This visit occurs after a 2-week washout period, and is the same as visit 1, only the supplement or placebo will be the one the subject was not assigned at study visit 1 (dietary supplement or placebo).

Study visit 4: This visit is the same as visit 2, and will be the end of the trial.

Blood testing: There is the possibility of infection and/or pain and bruising at the vein on the arm where the needle is inserted. Aseptic (sterile) technique and trained personnel minimize these risks.

Questionnaires: There are no known risks to completing the questionnaires

Measuring height, weight, blood pressure and pulse rate has no known risks

Actigraphy is wearing a wrist watch-like device that measures motion. Actigraphy has no known risks

Sleep Diary is to keep track of your sleep habits and experiences. There are no known risks in keeping a sleep diary.

Oximetry is a device that is worn on the finger like a thimble and measures the oxygen in your blood using a light. There are no known risks to wearing an oximetry device

Dietary Supplement is a mixture of 3 foods, a component of chicory, decaffeinated green tea powder and another component of green tea. The supplement has no known risks.

Ingredients: each bottle contains a mixture of 5 grams of collagen peptides, 5 grams of green tea extract, 1 gram of chicory extract, 7 grams of sweetener (half sugar and half erythritol), 0.2% potassium sorbate (as a preservative, 0.1% flavor, 60ml boiling water is added and cooled to 185 degrees F. 53 ml or 1.79 ounces is hot packed in a seal proof bottle that can be stored at room temperature or under refrigeration in this ready to serve format.

Dose: The total volume of each bottle is 53mL or 1.79 ounces and each bottle is one dose

Lot number: The lot number is 2008-1 for the supplement and 2008-2 for the placebo. The supplement and placebo were prepared on August 17, 2020

Preparation: The supplement and the placebo were prepared at the LSU Food Incubator.

Temperature: The supplement and placebo have been stored at room temperature.

Shelf-life: The shelf-life of the supplement is at least 2 years at room temperature. The product was hot packed and contains potassium sorbate which is a preservative for long-term storage. The expiration date for the supplement and placebo is August 17, 2022 and it is presently being stored in the Pennington pharmacy. The results of the stability study are attached.

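### Does the August 2022 expiry of the only described lots conflict with the hope of completing the study by the end of 2022?

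*Combined protocol and SAP*

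**What the plan says.** All references are to the combined protocol and SAP.

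- **Lot number and Shelf-life** (under Procedures Involved): one lot of each product is described, "The lot number is 2008-1 for the supplement and 2008-2 for the placebo". Both were prepared on August 17, 2020, with a shelf-life of two years or more at room temperature. The entry then fixes the limit: "The expiration date for the supplement and placebo is August 17, 2022". It also records that the product is held in the site pharmacy and that stability results are attached. Those results are not in the text available here, and that is not a defect of the plan.
- **Study Timelines**: "The Covid-19 problem has delayed the start of the study", followed by "we hope to complete the study by the end of 2022". The same section projects a duration: "We anticipate finishing the trial in 12 weeks, if we enroll a subject each week".
- **Number of Subjects**: "Ten subjects will be enrolled in this cross-over study consisting of a screening visit and four study visits".
- **Study Visit 2** (Study Visit 4 is the same): "The subject will return in 1 week (± 3 days) for a repeat polysomnography test".
- **Protocol Version Date**: "December 16, 2021".

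The text gives no first-dose date, last-enrolment date, last-dosing date, further lot or re-dating.

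**The concern.** The only dated completion target still in force lies 136 days after the only stated expiry date. The start had already slipped: the grant dates from February 2020, and by the version date 486 of the 730 days between preparation and expiry (67%) had gone. A reader can reasonably ask what happens if the start slips again.

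Either doses would be taken after the protocol's own expiry date, or dispensing would stop while some subjects had completed only one period. In the second case those subjects would give no supplement-placebo pair for the paired t-test named in Data and Specimen Management, in a trial of only ten.

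**Working it through.** **The plan's own figure.** August 17, 2020 plus two years is August 17, 2022 (730 days). The stated expiry date is reproduced exactly.

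**Time available.**

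- Version date to expiry: December 16, 2021 to August 17, 2022 = 244 days = 34.9 weeks.
- Version date to December 31, 2022 = 380 days. The part after expiry is 380 − 244 = 136 days, or 136/380 = 36%.

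**Time needed.** With ten subjects there are nine intervals between first baselines. Each course is 1 week of dosing + 2 weeks of washout + 1 week of dosing = 28 days.

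- Weekly enrolment: 9 × 7 + 28 = 91 days = 13.0 weeks.
- Both visits three days late: 63 + 34 = 97 days = 13.9 weeks. Both three days early: 63 + 22 = 85 days = 12.1 weeks.
- With 7 days of screening before the first baseline: 91 + 7 = 98 days = 14.0 weeks.

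**Slack before expiry.**

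- Nominal: 244 − 91 = 153 days (21.9 weeks). The latest first baseline is May 18, 2022 and the latest last baseline is July 20.
- Both windows late: 244 − 97 = 147 days. These dates become May 12 and July 14.

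**How slow could enrolment be?** The enrolment intervals other than 7 days are my assumptions.

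| Interval between subjects | Span (9 × interval + 28) | Latest first baseline |
|---|---|---|
| 7 days (the plan) | 91 days | May 18, 2022 |
| 14 days | 154 days | March 16, 2022 |
| 24 days | 244 days | December 16, 2021 |

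At half the planned rate, 244 − 154 = 90 days of slack remain.

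**Late starts (assumed; the documents give none).** If dispensing stopped at expiry, the number of subjects able to finish both periods would be:

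| First baseline | Finish both periods | Overrun if dosing continued |
|---|---|---|
| May 18 | 10 of 10 | 0 days |
| June 1 | 8 of 10 | 14 days |
| June 15 | 6 of 10 | 28 days |
| June 29 | 4 of 10 | 42 days |

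**Does a wider meaning of completion close the gap?** Study Timelines puts the report 4 weeks after study completion. Even if that report had to fit within 2022, dosing could still end 136 − 28 = 108 days after expiry. The gap between the two dates is therefore real; the question is whether the plan schedules dosing in it.

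**The case for a change.** The strongest case for a change is that the 12-week projection is conditional on weekly enrolment and has no start date, so it does not guarantee that dosing ends in time. The delay already recorded makes another one credible. A run timed to finish on December 31, 2022 would begin about October 1, wholly after expiry. If dispensing stopped partway, the standardized paired difference detectable with 80% power (two-sided 0.05) would rise from 1.00 with ten pairs to 1.16 with eight and 1.43 with six. About two sentences would settle the matter.

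Part of this stands. The protocol does not link the dosing calendar to the expiry date, and the end of 2022 does not by itself keep dosing before it. The attached stability results cannot be presumed to support a later date.

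The rest does not show a fault in the plan. A hoped-for outer date later than the expiry does not schedule any dose after it. The only duration the plan projects fits before expiry more than twice over (34.9 weeks against 13), and Resources Available expects no difficulty in recruiting. The lost pairs require both a start after mid-May and a halt in dispensing, and the documents state neither. The detectable differences add no weight: the Power analysis section calls this a pilot without a basis for powering, so there is no target from which they fall short.

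**Conclusion.** No change follows. The expiry date and the completion target can both hold, and on the plan's own enrolment rate they do so with about 22 weeks to spare at the version date. The result rests on one subject per week, a 28-day course, and a first baseline by about May 18, 2022 (May 12 if both windows run long). At half that rate the first baseline would have to fall by March 16, 2022.

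What remains is two small things. First, the link between dosing dates and expiry is unwritten. That is a detail of trial conduct: the date is printed in the protocol and the product sits in the site pharmacy. Should the start slip past mid-May, the sponsor would have to reconcile Study Timelines with the Shelf-life entry at that point; how to do so is not a statistical question. The endpoint, the crossover design and the paired comparison would read the same either way.

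Second, the projected 12 weeks is about one week short of the nominal 13 and just below the 12.1 weeks reached when both visits fall early. It is an anticipated duration that no analysis or decision uses, and either figure fits before expiry.

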Polysomnography (PSG) is an overnight video sleep study. PSG will include electroencephalography, electrooculography, electromyography, electrocardiography, pulse oximetry, nasal pressure transducer, oronasal thermocouple, calibrated respiratory inductance plethysmography. Sleep staging and events will be scored by registered PSG technologists according to established criteria.

Data and Specimen Banking

White blood cells called the buffy coat, serum from the blood and EDTA plasma will be stored for future tests related to the effect of the supplement on the white blood cells or serum. The white blood cells and serum will be frozen and used over a period of several months. Any extra material may be stored for future tests related to insomnia or the effect of the supplement on white blood cells or serum. The testing of the cells will be limited to the effect of the supplement on white blood cells and serum.

Power analysis.

No controlled trials of the supplement exist to power this study. This is a pilot study. If it is statistically insignificant, it will provide the basis for powering a definitive clinical trial.

Data and Specimen Management

The demographic data will be described using summary statistics. The comparisons of the supplement and placebo will be analyzed using paired t-testing. Data will be stored in the Pennington Data base that is controlled by the Research Computing Group and is password protected. Subjects in the trial will be given an A number which allows them to remain unknown to those analyzing the data. The data will be stored indefinitely as has all study data generated at Pennington. Buffy coats and serum will be stored at Pennington. The buffy coats and serum will be stored indefinitely and be used to analyze the effect of the supplement on white blood cell and serum related to sleep difficulty. Any data transfer will be done by the Pennington Research Computing Group.

Provisions to Monitor the Data to Ensure the Safety of Subjects

This is a minimal risk study, but the investigators will keep in close communication with the study coordinator to insure the study is executed properly and that the study participants are not having any concerning side effects.

Withdrawal of Subjects

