Subjects will be withdrawn from the study should it be determined by the medical investigator that the potential benefits of the study are out-weighed by side effects. Subjects may also be withdrawn from the study if they are unwilling or unable to comply with the study requirements.

Risks to Subjects

The only foreseeable risks of this study are those associated with drawing blood. There is the possibility of infection and/or pain and bruising at the vein on the arm where the needle is inserted. Aseptic (sterile) technique and trained personnel minimize these risks. The other procedures in this study have no known risks

Potential Benefits to Subjects

The subjects in this study may experience an improvement in their quality of life in the week they take the supplement. If that does occur, the effect is likely to go away after they are off the supplement for a day or two.

Vulnerable Populations

This study excludes vulnerable populations

Multi-Site Research

This is a single site study.

Sharing of Results with Subjects

The study findings will be shared with the study participants. We are expecting to present the study at a medical meeting and will share the abstract or press release with the study participants. The tests done in the study will be shared with the subjects and with their medical practitioner, if the patient wants that sharing to take place.

Setting

Page 7 of 9

The study will take place at the Pennington Center. Pennington coordinators and other health professionals are well-trained to conduct the procedures in this clinical trial.

Resources Available

We have done a study in which we recruited subjects with sleep difficulty. We have also developed a good relationship with [name], a sleep specialist. Between the patients with sleep problems wanting to enroll through information released by the Pennington Center and our relationship with the Sleep Center, we do not think that gathering study participants for the study will be difficult. Pennington has all the resources needed for this study.

Prior Approvals

We have received approval from the LIFT program with funding to complete the study.

Compensation

Participants will receive \$200 for completing the study.

Confidentiality

The study data will be stored indefinitely at Pennington in the database and in the medical records area. The data will be controlled by the Research Computing Group, and they will be responsible for any data transfer.

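### The only treatment comparison in this ten-subject, two-period crossover is a paired t-test with no period term, and equal numbers per order are not assured

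*Combined protocol and SAP*

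**What the plan says.** - **Analysis** (Data and Specimen Management): "The comparisons of the supplement and placebo will be analyzed using paired t-testing". Apart from summary statistics for demographics, this is the whole analysis text. No period, sequence or mixed-model term appears anywhere.
- **Size** (Number of Subjects): "Ten subjects will be enrolled in this cross-over study".
- **Allocation** (Study visit 1): "The study order of the supplement or placebo will be assigned randomly". No ratio, block size or balanced list is given.
- **Design** (Background): the trial is described as "comparing the supplement to a placebo after 1 week of administration separated by a 2-week washout period", which fits a comparison of end-of-period scores, although the analysis text does not name the score used.
- **Withdrawal** (Withdrawal of Subjects): "Subjects may also be withdrawn from the study if they are unwilling or unable to comply with the study requirements". There is no replacement rule.
- **Later use** (Power analysis): "If it is statistically insignificant, it will provide the basis for powering a definitive clinical trial".

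**The concern.** Each subject's supplement-minus-placebo difference is the treatment effect plus the period shift if placebo came first, and the effect minus the shift if the supplement came first. A paired t-test pools these differences as if they shared one mean. The shift drops out of the estimate only when the two orders are equal in number, and even then it stays in the error variance.

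A shift is plausible here, though not shown. Entry requires a minimum insomnia score and a minimum sleep-onset or wake time, so scores may regress toward the mean over the study. The end-of-period questionnaires follow the second and fourth laboratory nights, so familiarity with the laboratory and the forms differs between periods.

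Two things are at stake: the Chubon estimate and its power, with only ten subjects, and the standard deviation carried into planning the next trial. Carry-over is not part of this point. The protocol expects that "the effect is likely to go away after they are off the supplement for a day or two", and the washout is two weeks.

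**Working it through.** The plan states no alpha, effect size, standard deviation or power, so there is no figure to reproduce.

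**Inputs.** From the protocol: N = 10, two periods, two orders, paired t-test. Assumed: two-sided alpha 0.05; true effect 1.0; shift *s* (period 2 minus period 1) from 0 to 1.0. Effect and shift are in units of the within-order SD of the within-subject difference. The shift is in whichever score is analysed, taken here as the end-of-period score.

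**1. How often the orders balance.** If order is assigned by simple randomisation (an assumption), P(5:5) = 252/1024 = 0.246. A split of 6:4 or worse has probability 0.754, 7:3 or worse 0.344, and 8:2 or worse 0.109.

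**2. Bias in the split obtained.** With *a* subjects placebo-first and *b* supplement-first, the paired mean has expectation effect + *s*(*a* − *b*)/N. The bias is 0.2*s* at 6:4, 0.4*s* at 7:3 and 0.6*s* at 8:2 in absolute size; its sign depends on which order is larger.

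**3. Power at 5:5.** For the paired test, the mean is normal with variance 1/N. The sum of squares is noncentral chi-square on N − 1 df with noncentrality N*s*²[1 − ((*a* − *b*)/N)²]. The period-adjusted estimate is the unweighted mean of the two order-specific mean differences, with SE 0.5√(1/*a* + 1/*b*) on N − 2 df. At 5:5 that SE is 0.5√0.4 = 0.316, the same as 1/√10, so the term costs only one degree of freedom.

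| Shift (SD) | 0 | 0.1 | 0.25 | 0.4 | 0.5 | 1.0 |
|---|---|---|---|---|---|---|
| Paired, 5:5 | 0.803 | 0.800 | 0.783 | 0.750 | 0.720 | 0.482 |
| Period-adjusted, 5:5 | 0.791 | 0.791 | 0.791 | 0.791 | 0.791 | 0.791 |

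Simulation at shifts of 0, 0.25, 0.5 and 1.0 agrees (paired 0.804, 0.782, 0.720, 0.482; adjusted 0.790 to 0.792). The curves cross at a shift of about 0.20 SD (0.15 to 0.21 SD for effects of 0.6 to 1.2 SD).

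**4. Power averaged over simple randomisation.**

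| Shift (SD) | 0 | 0.25 | 0.4 | 0.5 | 1.0 |
|---|---|---|---|---|---|
| Paired | 0.803 | 0.779 | 0.743 | 0.711 | 0.500 |
| Period-adjusted | 0.741 | 0.741 | 0.741 | 0.741 | 0.741 |

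Without balancing, the term gains power only above about 0.41 SD. A 5:5 block plus the term (0.791) beats simple randomisation plus the paired test above about 0.18 SD.

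**5. Type I error of the paired test.** Averaged over simple randomisation it is 0.050 to 0.052. Given the split obtained, at a shift of 1.0 SD it is 0.007 (5:5), 0.017 (6:4), 0.063 (7:3) and 0.200 (8:2). The adjusted test holds about 0.050 in every case.

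**6. Standard deviation for the next trial.** At 5:5 the paired SD is inflated by √(1 + (10/9)*s*²): 1.03, 1.13 and 1.45 at shifts of 0.25, 0.5 and 1.0. Squared, the last two multiply a required sample size by about 1.3 and 2.1 if the next trial adjusts for period. For scale, sampling error alone puts an SD on 9 df at 0.55 to 1.45 times the truth.

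**The case against.** A paired t-test on a randomised crossover is a valid analysis, and this is a pilot with no power claim. The benefit of the period term rests on a shift that nothing in the documents quantifies, and the large contrast in power appears only when the shift is as big as the assumed effect. At 5:5 and 0.25 SD the gain is under one point. In an unequal split the unadjusted estimate has the lower mean squared error unless the shift exceeds √(0.25(1/*a* + 1/*b*) − 1/10) ÷ ((*a* − *b*)/10), which is 0.32 SD at 6:4 and 0.35 SD at 7:3. All of this stands. It limits the weight of the point and is the reason the term should not be added without balanced allocation.

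Chubon is also measured before each period, so a paired test on change from each period's own baseline would remove a constant shift in level. That is correct, but a difference between periods in the change itself would remain. The protocol does not specify change scores, and its Background wording fits end-of-period scores.

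The SD argument is modest beside sampling error. The unadjusted SD is roughly right if the next trial is also analysed by paired t-test with the same shift. It is the wrong one if that trial adjusts for period or has no such shift.

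Finally, a blocked list may exist unwritten. If so, stating it settles the allocation half of the point.

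**Conclusion.** The point holds as a recommended improvement, with moderate confidence. The plan is not invalid: over repeated randomisation the paired test is unbiased with type I error near 5%. It does leave this one trial's estimate exposed to any period shift if the orders are unequal, and its power and SD exposed even if they are equal. On the assumptions above, balancing and adjusting together cost 1.2 points of power at 5:5 when there is no shift. Against a plan already at 5:5 they gain about 7 points at 0.5 SD and 31 at 1.0 SD. The size of the benefit rests on the assumed shift and effect, on analysis of end-of-period scores and, for the averaged figures, on simple randomisation.

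**What to change.** 1. State that order is allocated from a permuted block with five subjects per order.
2. Replace the paired t-test for Chubon and the continuous secondary endpoints with a period-adjusted analysis of end-of-period scores. Either compare within-subject period differences (period 1 minus period 2) between the two orders by a two-sample t-test, halving the difference to get the treatment effect, or fit a mixed model with treatment and period fixed and subject random. The two agree on complete data but can differ after a dropout, so name one in advance.
3. Report the estimate, its 95% CI and the period-adjusted within-subject SD, and use that SD to size the later trial if it too will have a period term.

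The cost is two sentences and a blocked list. If there is no shift, power goes from 80.3% to 79.1% at 5:5, and from 74.8% to 72.5% if one subject is lost (5:4). Without blocking the cost is larger (80.3% to 77.4% at 6:4, to 71.9% at 7:3), so items 1 and 2 belong together.
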